#### Attachments

Attach Type	File Name
DataCollection	Semi-structured qualitative interview guide 9.24.21 patient.docx
DataCollection	Semi-structured qualitative interview guide 9.24.21 clinician.docx
DataCollection	ColumbiaForPsychiatryStudy.docx
DataCollection	CBTSQ-BA.docx
DataCollection	CEQ.docx
DataCollection	DASS-21 - Depression Anxiety Stress Scale - 21 item.docx
DataCollection	Evidence-based Practice Attitude Scale (EBPAS).docx
DataCollection	Hope Scale.docx
DataCollection	MEAQ- Multidimensional Experiential Avoidance Questionnaire.docx
DataCollection	PAI-BOR.docx
DataCollection	UCLA Loneliness-3.docx
DataCollection	WAI-SR Client Version.docx
DataCollection	DecisionSelfEfficacy_Personali.pdf
DataCollection	URICA_PersonalizationAtUKPsych (1).pdf
DataCollection	InitialTreatmentPreferencesQue.pdf
DataCollection	HAM-A.doc
DataCollection	CSQ8_PersonalizationAtUKPsychi.pdf
DataCollection	CGI.pdf
DataCollection	UP-CSQ.pdf
DataCollection	PatientPostTxFeedbackForm_Pers (1).pdf
DataCollection	HAM-D.doc
DataCollection	Post-Treatment Therapist Feedback Form_Tracked.docx
DataCollection	Post-Treatment Therapist Feedback Form_Clean.docx
DataCollection	A1 Medication list.docx
DataCollection	3 Concurrent Treatment Form.docx
DataCollection	ASI.pdf
DataCollection	EPQR-S- Eysenck Personality Questionnaire Revised- Short-Form.pdf
DataCollection	IIP-BPD.pdf
DataCollection	NEO-FFI.pdf
DataCollection	NEO-PI-R-N - Neuroticism and facets.pdf
DataCollection	OASIS-Overall Anxiety Severity and Impairment Scale.pdf
DataCollection	ODSIS- Overall Depression Severity and Impairment Scale.pdf
DataCollection	PANAS - Positive and Negative Affect Schedule.pdf

DataCollection	Q-LES-Q - Quality of Life and Enjoyment and Satisfaction Questionnaire.pdf
DataCollection	SMQ - Southampton Mindfulness Questionnaire.pdf
DataCollection	TIPS DIAMOND.pdf
DataCollection	WSAS-CR.pdf
DataCollection	BES - Beliefs about Emotions Scale.pdf
DataCollection	Post-workshop provider feedback.docx
DataCollection	Therapist Demographics Form.docx
DataCollection	Motivation to Learn Scale-2.doc
DataCollection	Therapist Knowledge Acquisition.docx
DataCollection	Self-perceptions of skills use.pdf
DataCollection	Demographics_TreatmentPersonal.pdf

## Resources

Describe the availability of the resources and adequacy of the facilities that you will use to perform the research. Such resources may include:

- Staffing and personnel, in terms of availability, number, expertise, and experience;
- Computer or other technological resources, mobile or otherwise, required or created during the conduct of the research;
- Psychological, social, or medical services, including equipment needed to protect subjects, medical monitoring, ancillary care, or counseling or social support services that may be required because of research participation;
- Resources for communication with subjects, such as language translation/interpretation services.

**Personnel:** The PI is a licensed clinical psychologist with 15 years of clinical experience providing evidence-based care to individuals with anxiety, depressive, and related disorders. The PI is also a co-developer of treatment provided in this study and has ample experience training others in its provision. The PI's team currently includes one post-doctoral scholar with a PhD in clinical psychology and 6 years of experience providing evidence-based therapy and several doctoral students in clinical psychology. These individuals will, under the PI's supervision, conduct assessments and support the clinician participants who will be receiving training in the study intervention. The team also includes several undergraduate research assistants to conduct phone screens (under supervision) and complete day-to-day study management tasks. The Co-PI, located at Suffolk University, is a licensed clinical psychologist with over 10 years of experience conducting qualitative interviews with participants providing and/or receiving psychotherapy treatment. The Co-PI will assume a leading role in administering the qualitative interviews and focus groups. The Co-PI's team currently includes two doctoral students in clinical psychology at Suffolk University. These students will, under the PI and Co-PI's supervision, conduct qualitative interviews and focus groups with clinician and patient participants after receiving training from the Co-PI in the administration of qualitative interviewing techniques.

**Facilities:** This study will take place through UK Psychiatry. As noted in the letter of support from [name], the medical director of the Adult Outpatient Service, our team will be provided with space and/or UK HealthCare Zoom access, to facilitate the conduct of this project. The PI also has dedicated technology resources (computers, study iPad) to facilitate the use of our online data management service, licensed by UK (REDCap). Additionally, the PI has several audio-recording devices to tape therapy sessions.

## Potential Risks & Benefits

### Risks

- Describe any potential risks – including physical, psychological, social, legal, ability to re-identify subjects, or other risks. Assess the seriousness and likelihood of each risk.
- Which risks may affect a subject's willingness to participate in the study?
- *Qualitative research* - describe ethical issues that could arise while conducting research in the field and strategies you may use to handle those situations.
- Describe any steps to mitigate these risks.

### Benefits

- Describe potential direct benefits to study participants – including diagnostic or therapeutic, physical, psychological or emotional, learning benefits. This cannot include incentives or payments.
- State if there are no direct benefits.
- Describe potential benefits to society and/or general knowledge to be gained.

Describe why potential benefits are reasonable in relation to potential risks. If applicable, justify why risks to vulnerable subjects are reasonable to potential benefits.

The primary risk in the current study is termination of treatment before symptom remission is achieved for those in the Brief condition. Participants will be informed about this risk on the phone screen and at Assessment Visit 1. It is important to note, however, that the average number of sessions community patients typically attend is 5, which suggests that this risk may be no greater than what is experienced in usual care. Additionally, a large proportion of symptom improvement occurs within the first 5 sessions of treatment (Fennell & Teasdale, 1987; Lutz, Stulz, & Köck, 2009), further mitigating this risk. Finally, in the event that participants in the Brief treatment are at an imminent risk of harm to themselves or others at their final session, they will be brought to the attention of the PI to

develop a safety plan with the participant which may include referrals to other psychotherapy resources or hospitalization.

Participants may experience some interference with daily activities due to scheduling of sessions. Additionally, some patients may find answering the questionnaires uncomfortable because of the sensitive nature of some of the questions (e.g., asking about symptoms of anxiety). In any of the modules the primary risk is the evocation of uncomfortable levels of anxiety or other emotions during the sessions. Some patients may find sessions stressful and react to them with anxiety. However, it is not expected that anxiety will be higher than would be experienced in real life situations or in the course of usual and customary clinical treatment. Participants will be informed about these risks and told that they may withdraw from the study at any time and may refuse to complete any procedures they find too uncomfortable.

There is also risk of a breach of confidentiality. Every precaution will be taken to protect participant's confidentiality. Paper data will be stored in locked cabinets and electronic data will be stored in password protected files. Additionally, each participant will be assigned a unique study ID number and this number will appear on all of his or her assessments. Information linking the study ID to the participant will be housed separately from the data. Participants who choose to engage in remote sessions will use secure electronic communications (e.g., phone calls or Zoom via the UK HealthCare portal). Despite all of these precautions, a breach of confidentiality remains a risk inherent in the research. Participants will be informed of this risk, as well as the measures in place to avoid such a breach, in the informed consent form.

The primary risk for clinician participants is the the time burden associated with the study (i.e., filling out questionnaires, attending consultation calls and the training workshop). Every effort has been made to minimize the number of questionnaires that clinicians are asked to complete. Although the training workshop and consultation calls are time-consuming, clinicians may benefit/enjoy these educational experiences.

Study participants may directly benefit from the skills that they learn from treatment. These skills (i.e. mindfulness, psycho-education, cognitive restructuring, and countering emotion-drive behaviors) have been shown to help reduce the symptoms of anxiety disorders. Therefore, it is possible that patients who take part in this study will obtain some relief from symptoms of anxiety and associated distress during the duration of this study. The risk of loss of confidentiality and mild emotional distress from filling out questionnaires and engaging in treatment are no more than patients would experience during routine care for emotional disorders. Additionally, this study will allow us to increase our knowledge of how to increase treatment efficiency by systematically exploring different methods of treatment-delivery based on a patient's presentation (i.e., focusing on strengths or weaknesses). Clinician participants may benefit from training in cutting edge advances in the provision of cognitive behavioral therapy that may enhance their practices.

#### Available Alternative Opportunities/Treatments

Describe alternative treatments or opportunities that might be available to those who choose not to participate in the study, and which offer the subject equal or greater advantages. If applicable, this should include a discussion of the current standard of care treatment(s).

The treatment provided in our research study is very similar to the standard of care. If potential participants choose not to provide their informed consent, or if participants withdraw, they can continue to pursue care at UK Psychiatry.

[Back to Top](#)

#### Records, Privacy, and Confidentiality

Specify where the data and/or specimens will be stored and how the researcher will ensure the privacy and confidentiality of both. Specify who will have access to the data/specimens and why they need access.

Describe how data will be managed after the study is complete:

- If data/specimens will be maintained, specify whether identifiers will be removed from the maintained information/material.
- If identifiers will not be removed, provide justification for retaining them and describe how you will protect confidentiality.
- If the data/specimens will be destroyed, verify that this will not violate [retention policies](#) and will adhere to applicable facility requirements.

If this study will use de-identified data from another source, describe what measures will be taken to ensure that subject identifiers are not given to the investigator.

If applicable, describe procedures for sharing data/specimens with collaborators not affiliated with UK.

For additional considerations:

[Return of Research Results or Incidental Research Findings](#)

[HIPAA policies](#)

[FERPA policies](#)

[Procedures for Transfer agreements](#)

[Information regarding multi-site studies](#)

[NIH Genomic Data Sharing \(GDS\) Policy](#)

[Digital Data](#)

Data includes participants' self-reported questionnaire responses, clinician-rated interview responses, and audio tapes from sessions, assessments, qualitative interviews, and focus groups. This information is necessary to answer the proposed research questions and ensure fidelity to the treatment being delivered. Session recordings will be collected via HIPAA-compliant UK HealthCare's Zoom

software and stored directly on UK HealthCare's HIPAA-compliant cloud servers.

Please note: (1) no member of the study team (none of whom are part of the covered entity) would access study subjects' medical records through UK HealthCare, (2) no information obtained from patient subjects during the course of the research project would go back into their UK HealthCare medical records, and (3) no information from the interview or focus group activities conducted by Suffolk staff would go back into patient subjects' UK HealthCare medical records.

Physical data will be stored in locked cabinets and electronic data will be stored in password-protected databases online (via REDCap and downloaded onto local computers connected to and protected by the University of Kentucky network). All data will be de-identified and assigned a unique participant ID number. This number will appear on all study forms. The information linking this number to any identifying information will be stored in a separate file on a local computer hard-drive. Only study staff and UK institutional oversight (i.e., IRB personnel) will have access to identifying information or the information linking the ID number to the participant. Following completion of the study, the key linking participants identities to their data will be destroyed. Final online data will be downloaded from the REDCap server and saved to password-protected local computer hard drives; remaining data on the REDCap server will be deleted. De-identified (i.e., labeled with participant code) paper and electronic data will be maintained for at least six years after the study's closure or at least seven years after the last patient is seen (whichever comes first) through the National Institute of Mental Health Data Archive. Any publications based on this data will not include identifying information. Patients will be made aware of this information in the consent form.

Suffolk University-based study staff will access electronic data via remote access to the authorized UK servers. Suffolk staff have received LinkBlue IDs and been authorized by UK, UK IT, and the PI to access this information for the purposes of this study. These study staff members will complete all interviews remotely via the UK HealthCare Zoom portal and save the recordings of these interviews directly onto the authorized UK server using their LinkBlue access.

Focus groups present and inherent limitation to confidentiality in that we cannot control what participants say about the focus groups after the fact. Study staff will clearly state this at the start of the focus group and remind participants during the group. We have also included language about this limitation in the informed consent form that all participants will review before engaging in any study procedures.

The following procedures will be used to minimize risks for participants:

1. Study exclusion criteria precludes any patients who are currently experiencing imminent suicidal risk. In addition, the study will also exclude individuals who might require more immediate and/ or intensive treatment for more severe clinical difficulties.
2. Although unlikely, risk issues may arise over the course of study participation. The PI (a licensed clinical psychologist with nearly 15 years working with high risk patients) will conduct regular, weekly meetings with research staff and clinician participants. At these meetings, any concerns regarding patient safety will be fully discussed, and the PI will intervene as clinically indicated.
3. Moreover, any patient showing significant deterioration or developing active suicidal potential as judged clinically by the clinician, the PI, and the director of outpatient services at UK Psychiatry will be removed from the study and will be referred for immediate and intensive clinical intervention. The PI will review any adverse events that occur during the course of the study.
4. The clinician participants in this study, who will be providing care to the study patients, are licensed mental health professionals. The study assessors (graduate students and post-docs) and well-trained and experienced, and will be working under the direct supervision of the PI.
5. For participants engaged in remote sessions, they will only be contacted via secure electronic means (e.g., telephone or Zoom via the UK HealthCare portal).
6. Post-treatment qualitative interviews will be conducted through the UK HealthCare HIPAA-compliant Zoom portal. This is to ensure recordings of interviews can be saved directly to UK-controlled servers with password protection.
7. During post-treatment focus groups with patient participants, we will remind them of the limits of confidentiality in that we cannot control whether other participants share information from the focus groups. We will also ask that all participants respect the privacy and confidentiality of focus group members. We will make it clear that, because we are not accessing patients' medical records, no information obtained through the interview or focus group activities will be entered into patients' UK HealthCare medical records.
8. During post-treatment focus groups with clinician participants, we will specifically ask them not to share patient PHI so as to protect the privacy and confidentiality of patient participants. We will remind clinician participants about this request throughout the focus groups.
9. As in any clinical research program, participant (patients and clinicians) confidentiality will be carefully guarded and respected. All data with identifying information will be stored in locked files and all other data will be identified with subject identification codes (see Confidentiality section below for full procedures).
10. Finally, all participants (patients & clinicians) will be clearly informed of their right to withdraw from the study at any point.

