**Patient Participants:**

**Inclusion Criteria:** We aim to recruit individuals diagnosed with at least one emotional disorder will be eligible to participate. Specifically, emotional disorders include DSM-5 anxiety disorders, obsessive-compulsive disorders, and trauma- and stressor-related disorders. These individuals will be 18 years of age or older and fluent in English. Patients on psychotropic medications will be included if they are willing to maintain a stable dosage throughout the study period; this procedure allows for a broader range of participants and avoids having outcomes assessment confounded by the initiation of medication during treatment. Finally, patients must be willing to refrain from additional treatment for the duration of the study. Medication stability and exclusion of individuals in concurrent therapy are long-standing inclusion criteria in clinical trials conducted by the PI (see Barlow et al., 2017)

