Following Assessment Visit 1, all participants will begin completing weekly treatment sessions in person, via phone, or via HIPAA-compliant video conferencing service (i.e., Zoom via the UK HealthCare portal); the order of treatment skills will be determined based on their assignment to module-ordering condition. Before the start of Treatment Session 5, clinician participants will alert study staff (i.e., research assistant) to request a randomization to a Treatment Length Condition: Brief (6 sessions) or Full (12 sessions). Treatment Length Randomization will occur at this stage to limit expectancy effects on therapists' and participants' behaviors, while also allowing therapists and participants to plan their final 2 sessions together with this randomization in mind. Participants randomized to the Brief treatment condition be reminded during Treatment Session 6 how they can use the skills learned in the previous sessions in the upcoming weeks to prevent relapse. In the event that participants are at an imminent risk of harm to themselves or others at this session, the therapist will work with the PI to develop a safety plan with the participant which may include referrals to other psychotherapy resources or hospitalization.

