Regardless of randomization, all participants will be scheduled for Assessment Visit 2 to occur between treatment sessions 5 and 6. Participants will complete an interview-based diagnostic assessment with a study assessor that will focus on the diagnoses assigned at Assessment Visit 1. This assessment may take place in person at UK psychiatry, over the phone, or via HIPAA-compliant Zoom. This assessment visit will be audio-recorded. Participants will also complete the same battery of self-report questionnaires at this visit as at Assessment Visit 1. All participants will also complete Assessment Visit 3, which will take place between weeks 13-16 (corresponding to the end of the treatment window for the Full length condition). This assessment visit will also be audio-recorded and may take place in person at UK Psychiatry, over the phone, or via HIPAA-compliant Zoom. Finally, Assessment Visit 4 will take place (in person at UK Psychiatry, over the phone, or via HIPAA-compliant Zoom) between 46 and 50 weeks after Assessment 1 and will include the same questionnaires.

Following the last treatment session (Treatment Session 13 for participants in the Full treatment condition; Treatment Session 7 for participants in the Brief treatment condition), participants will be asked to provide satisfaction ratings and written qualitative feedback on their experience with the treatment they received. Additionally, all participants will be asked to complete a weekly self-report battery assessing symptoms, skill proficiency, and skill knowledge for 20 weeks (again corresponding to the treatment window for the Full length condition); patients in the Brief condition will continue to complete these questionnaires after discontinuing treatment. These questionnaires will be emailed to participants and we will ask that they are completed within two days of receipt.

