All self-report questionnaires will be completed online via REDCap. This survey platform is designed specifically for collection of research data, and therefore meets the privacy standards imposed on health care records by the Health Insurance Portability and Accountability Act (HIPAA). For Assessment Visits (1-4) that take place at UK psychiatry, self-report batteries will be completed on-site using a study iPad. The battery administered weekly between treatment sessions, along with the Assessment visits that take place remotely, will be emailed to participants to be completed on their own devices. Finally, although we anticipate that most patients will prefer to complete these measure electronically, we can provide paper and pencil versions of the questionnaires if requested.

There may be circumstances in which study patients are referred for additional care (i.e., they finish all study procedures and request a referral, they are withdrawn due to deterioration and given referrals to immediate treatment). No written information from the official study record (i.e., self-report questionnaire scores, assessor ratings) would be shared with UKHealthcare, or any other outside provider, upon referral after study. However, to streamline care, we will instruct the patient to ask their new provider to serve the study with a medical release of information (signed by the new provider and the patient) that allows their study clinician to speak with their new provider and provide clinical impressions. The release of information is a standard form for medical practitioners in routine care; since this is a not a study document, we have not attached it here.

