### Data Collection & Research Materials

In this section, please provide the following:

- Describe all sources or methods for obtaining research materials about or from living individuals (such as specimens, records, surveys, interviews, participant observation, etc.), and explain why this information is needed to conduct the study.
- For each source or method described, please list or attach all data to be collected (such as genetic information, interview scripts, survey tools, data collection forms for existing data, etc.).
- If you will conduct a record or chart review, list the beginning and end dates of the records you will view.

Data collection will be accomplished via phone screening questions, diagnostic interview, and self-report questionnaires attached below. Through these measures we will collect data regarding participants' experiences with psychological symptoms, life functioning, and interpersonal interactions throughout the study.

The measures will be administered to patients according to the following schedule:

Assessment Visits:

DIAMOND

Demographic form (A1 only)

OASIS

ODSIS

UCLA Loneliness-3

DASS

WSAS-CR

Q-LES-Q

MEAQ

PANAS

BES

SMQ

ASI

PAI-BOR

NEO-FFI

EPQR-S

IIP-BPD

NEO-PI-R-N

CBTSQ-BA

Hope Scale

Medication list (Assessment Visit 1 only)

Concurrent Treatment Form (Assessment Visits 2, 3, and 4 only)

Feedback Form (post-Assessment Visit 3 only)

URICA (Assessment Visit 1 only)

Decision-making self-efficacy scale (Assessment Visit 1 only)

Initial Treatment Preferences Questionnaire (Assessment Visit 1 only)

C-SSRS - Full measure

HAM-A

HAM-D

CSQ-8 (Assessment Visit 3 only)

Patient Post-Treatment Feedback Form (Assessment Visit 3 only)

Pre-Session (Weekly):

OASIS

ODSIS

UCLA Loneliness-3

MEAQ

PANAS

BES

SMQ

CBTSQ-BA

MEAQ-BA

ASI

Self-perception of Skill Use

C-SSRS items 1-6

UP-CSQ

Post-Session (Weekly):

WAI-SR  
CEQ (post-1st session only)

The following measures will be administered to clinicians according to the following schedule:

During initial visit (after informed consent):

EBPAS  
Motivation to Learn Scale  
Therapist Demographics

After the didactic workshop:

Post workshop provider feedback  
Therapist Knowledge Acquisition quiz

After each patient has completed treatment:

CGI

After all study patients on the clinician's caseload completes their last session:

Provider feedback form

Qualitative Interviews for:

Patient Participants  
Clinician Participants

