**Pilot Test of Personalization Aims (ordering and discontinuation).** In addition to our primary aim of establishing the feasibility/acceptability of our personalization strategies and study design, we seek to determine whether a preliminary signal exists to support the notion that personalized sequencing and target-informed discontinuation can enhance treatment efficiency. First, to explore whether personalized sequencing leads to more efficient improvements in the core process addressed by the UP, we will use hierarchical linear mixed modeling (HLMM) to compare the average rate of change in clinical outcomes among the three UP sequencing conditions (UPS, UPP-CA, and UPP-CO). The primary outcome measure for aim is the distress aversion subscale from the MEAQ (MEAQ-DA), which has previously been used to demonstrate target engagement with the UP (see Preliminary Studies). Additionally, to examine whether core process engagement can serve as an early indicator of treatment response, prompting discontinuation, we will assess variability in MEAQ-DA levels at the second stage randomization (S5 assessment), along with the degree to which any patients randomized to discontinue demonstrate additional symptom improvement (using HAM-A ratings) in the absence of treatment such that they are responders by the W20 assessment. We will also explore whether patterns exist between S5 MEAQ-DA scores and responder status for those that discontinued after session 6.

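### Patients who deteriorate are removed from the study rather than from study treatment only, so their later-course and acceptability data are lost (minor, cheap to fix)

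*Combined protocol and SAP*

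**What the plan says.** Item 3 of the risk-minimizing procedures (Records, Privacy, and Confidentiality) covers patients in either length arm who clearly worsen or become actively suicidal, in the joint judgment of the clinician, the PI and the outpatient director. Such a patient "will be removed from the study and will be referred for immediate and intensive clinical intervention".

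Research Procedures gives two examples of patients referred for further care. One is the patient who completes everything and asks for a referral. The other is the case where "they are withdrawn due to deterioration and given referrals to immediate treatment". The same section uses the word withdrawn for patients found ineligible after Assessment Visit 1, who leave the study altogether.

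Elsewhere the plan separates the end of treatment from the end of follow-up:

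- Under Research Procedures, "patients in the Brief condition will continue to complete these questionnaires after discontinuing treatment".
- For a Brief patient at imminent risk at the final session, the therapist works with the PI to "develop a safety plan with the participant which may include referrals to other psychotherapy resources or hospitalization". No removal is mentioned.
- The Concurrent Treatment Form is scheduled at Visits 2, 3 and 4 (Data Collection & Research Materials), so outside care can already be recorded.

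The Statistical Design section asks whether "any patients randomized to discontinue demonstrate additional symptom improvement (using HAM-A ratings) in the absence of treatment", judged by responder status at week 20. Under Study Feasibility it reports treatment and assessment completion rates, but it does not ask for removals by arm.

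**The concern.** Removal is triggered by a bad clinical course, so whatever it makes missing is missing for a reason tied to outcome. The plan itself says that "The primary risk in the current study is termination of treatment before symptom remission is achieved for those in the Brief condition". A trial of early discontinuation should therefore be able to show what happened to patients who got worse, how they rated the treatment, and what care they then received.

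Feasibility and acceptability are the primary aim, and Power Analyses says that the pilot is meant to inform a later, well-powered trial. If the patients who did worst give no satisfaction rating, feedback form or interview, the acceptability picture comes only from those who did better, and the rule may be carried into the larger trial.

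**Working it through.** The plan gives no removal rate, dropout rate or missing-data figure on this point, so there is no stated number to reproduce.

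**Step 1: does the text keep removed patients in assessment?** Item 3 says removed from the study, and Research Procedures says withdrawn, in contrast to patients who complete everything. No available section provides for assessment after such a withdrawal. The plain reading is full exit, although no sentence says outright that assessments stop.

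**Step 2: what would be lost under that reading?**

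Inputs, from Research Procedures and Data Collection & Research Materials:

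- The weekly battery, which includes the MEAQ, runs for 20 weeks.
- Visit 2 falls between Sessions 5 and 6. Visits 3 and 4 follow.
- HAM-A is listed at Assessment Visits only.
- The CSQ-8 and the patient feedback form are given at Visit 3 only.
- Patient interviews are held at week 20.
- Assumption: one session a week, with the battery for the week of removal completed.

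Batteries lost = 20 − week of removal.

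- Week 5, before Visit 2: 20 − 5 = 15, and 15/20 = 75%. Visits 2, 3 and 4 are lost (3 of 3), so there is no post-baseline HAM-A.
- Week 7, after Visit 2: 20 − 7 = 13, and 13/20 = 65%. Visits 3 and 4 are lost (2 of 3).
- In both cases the Visit 3 acceptability measures are lost, and possibly the interview.

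**Step 3: how many patients?** Item 2 of the same list calls risk issues unlikely. The length randomization comes before Session 5. Brief treatment ends at Session 6 or 7 (the plan gives both), so Brief patients then have 6 − 4 = 2 or 7 − 4 = 3 sessions left. Full patients have 12 − 4 = 8 or 13 − 4 = 9. Weekly C-SSRS items could still prompt a removal later. The number may be near zero.

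**Step 4: could the week-20 responder description be materially biased?** Only if it were computed on observed cases, which the plan does not state. Suppose n Brief patients, a true responder rate p, and k removed patients, none of whom respond. The observed rate is p·n/(n − k). Take n = 25 and 40, half of the 50 enrolled (Subject Info To-Date) and of the maximum of 80 (Project Information), assuming equal allocation. Take p from 40% to 60%, also assumed.

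- k = 1: n = 40, p = 0.40 gives 16/39 = 41.0% (+1.0 points). n = 25, p = 0.60 gives 15/24 = 62.5% (+2.5).
- k = 2: n = 40, p = 0.40 gives 16/38 = 42.1% (+2.1). n = 25, p = 0.60 gives 15/23 = 65.2% (+5.2).
- The 95% half-width at 50% is 1.96·√(0.25/n): 19.6 points for n = 25 and 15.5 for n = 40.
- Setting 0.5·n/(n − k) − 0.5 equal to the half-width gives k = 7.0 of 25 or 9.5 of 40.

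Study Design also gives a total of 150. At n = 75, one removal with p = 0.60 gives 45/74 = 60.8% (+0.8), which is smaller still.

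**The case against.** The strongest reply is that the point rests on silence. Item 3 belongs to a list of safety measures, and the line in Research Procedures is an aside about sharing records on referral. The visit schedule is written for all participants, and the consent pages, where follow-up after withdrawal is often described, were not available. This stands as a limit on certainty. It does not supply a provision for follow-up, and if follow-up is intended, one sentence settles the matter.

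A second reply is that the lost data feed no planned analysis shown to be damaged. This largely stands. A reader might infer that the MEAQ-DA slopes are biased. A likelihood-based mixed model uses the scores up to removal, and nothing in the documents shows material bias. A reader might also infer an inflated responder rate, but that needs an observed-case analysis the plan does not state, and Step 4 shows how small the shift would be. Nor is a Brief-versus-Full responder contrast at risk, because none is planned. Later HAM-A scores obtained under referral care would not answer a question about improvement without treatment.

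Third, the events themselves are not lost. The PI reviews adverse events, and the continuing-review form asks for an explanation of patients withdrawn by the PI for safety or welfare. That is correct, but neither gives the later course or the patient's view of the treatment.

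Fourth, continued follow-up has a safety cost. The weekly battery contains C-SSRS items, and written study information is not passed to outside providers on referral. This is a real cost and is counted under the fix. It is limited, because the schedule already collects these items from Brief patients after their treatment ends.

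**Conclusion.** The point holds as a minor, inexpensive improvement, with medium confidence. Followed as written, the plan takes deteriorating patients out of the study, and nothing available keeps them in assessment. For each such patient, on a weekly schedule, removal in weeks 5 to 7 costs 65% to 75% of the weekly batteries, two or three of the three post-baseline visits, the Visit 3 acceptability measures, and possibly the interview.

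The harm is a gap in the acceptability and later-course data among those who did worst. It is not a demonstrated bias in any efficacy result. The conclusion rests on reading removal as full exit, on the absence of a contrary provision in the unavailable consent pages, and on few removals.

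**What to change.** 1. **Research Procedures and item 3.** State that removal for deterioration ends study treatment only and that the referral is unchanged. Offer the remaining Assessment Visits and questionnaires by phone, Zoom or online, if the patient agrees and it is clinically appropriate.
2. **Additional treatment.** Eligibility requires that "patients must be willing to refrain from additional treatment for the duration of the study". State that accepting the referral does not breach this for the purpose of follow-up, and record the care on the existing Concurrent Treatment Form.
3. **Statistical Design.** Keep everyone randomized to discontinue in the responder denominator, and count patients referred for deterioration before week 20 as non-responders. This fits the question about improvement without treatment and needs no extra data.
4. **Reporting.** Give removals by arm and by timing relative to the length randomization.

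The cost is a sentence or so in each place and a few remote contacts with instruments already scheduled. Unwell patients bear some burden and may decline. Whatever response is used for C-SSRS answers from Brief patients after treatment ends must also cover referred patients. With 50 patients already enrolled, the follow-up change may reach only some of them. Items 3 and 4 remain worthwhile at any time before analysis.
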